7.1 Specification of Safety Parameters

[name] will create a data use agreement with UCH in order to receive the MDS 3.0 and electronic health records data. [name] will merge these data sets, add a unique identifier to the data set, and remove face identifiers such as name, SSN, HIC prior to providing it to the statistical consultant via a secure file transfer. These efforts will protect participant privacy. The Biostatistician will direct the statistical consultant on conducting the analysis, but will not have access directly to the data.

We will also provide a help line for the implementation team to contact the project manager or PI at any time if they need assistance in problem solving to modify an IPPI for a resident to their remaining strengths during the course of implementation.

We will plan for monthly check-in calls with the implementation team to see if they have any concerns and check-in on implementation progress. Residents have the ability to decline to participate in any offered IPPI activity.

All other safety parameters will be in line with safety and health regulations as set forth by the NHs themselves. Each NH is regulated by the Centers for Medicare and Medicaid Services and will be expected to follow all clinical safety and reporting guidelines during the duration of this study.

7.2 Methods and Timing for Assessing, Recording, and Analyzing Safety Parameters

Safety concerns for the IPPI intervention are no more than those experienced in usual care for NH residents. NH Residents: The IPPI program will be implemented by staff as part of the nursing home resident's clinical care needs. The IPPI activities involve no more than minimal risk to the NH resident as these activities are typically done by care partners as part of standard of care. The care partner will be taught to use the good communication practices taught in the emotion-focused communication training to deliver activities that are preferred by residents. Each NH has a responsibility, as regulated by the Centers for Medicare and Medicaid Services to follow specific safety protocols and reporting guidelines. Each NH will continue to follow these protocols while delivering the IPPI intervention. The IPPI involves minimal risk since the resident can decline and is based on his or her preference, would not adversely impact the rights and welfare of residents because it would involve a meaningful and enjoyable use of time with a care partner, the legally authorized representative would be informed about the new clinical activity being tried with their loved one/client as is the case with any new clinical activity being implemented with individuals, and deidentified data will be provided from the provider organization.

7.3 Adverse Events and Serious Adverse Events

Adverse and serious adverse events for this study are defined as follows:

Adverse Event (AE): Any unfavorable medical or behavioral outcome in a clinical research study participant, including but not limited to expression of extreme distress (defined as a person specific change in behavior that is uncharacteristic of the individual

whereby the individual is visibly upset and/or inconsolable), an illness event (i.e., a heart attack, stroke), or a fall temporally associated with the participants' involvement in the research, whether or not considered related to participation in the research.

Serious Adverse Event (SAE): Any adverse event that:

- Results in death
- Is life threatening, or places the participant at immediate risk of death from the event as it occurred
- Requires or prolongs hospitalization
- Causes persistent or significant disability or incapacity
- Is another condition which investigators judge to represent significant hazards

Unanticipated Problem (UP) Definition: Any incident, experience, or outcome that meets all of the following criteria:

- Unexpected, in terms of nature, severity, or frequency, given (a) the research procedures that are described in the protocol-related documents, such as the IRB-approved research protocol and informed consent document; and (b) the characteristics of the study population;
- Related or possibly related to participation in the research;
- Suggests that the research places participants or others at a greater risk of harm (including physical, psychological, economic, or social harm) than was previously known or recognized.

Adverse events are not anticipated to occur in response to the intervention beyond the routine experience of events in clinical care. We expect no SAEs to occur as a result of an IPPI activity because they are meant to be short, enjoyable activities. We would expect that due to the age and illness severity of the people living with dementia that the possibility of falls, emergency room/hospitalizations, and death can reasonably be expected. During our monthly check-in calls with the implementation team, we will ask if any adverse events have occurred, *“Have there been any unexpected changes in resident behaviors or health while participating in the study?”*

NHs will otherwise follow their regulated health and safety protocols and responses.

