However, a person could become agitated during an IPPI if it is not explained well by a care partner, as with routine care. In these instances, behaviors such as wandering or becoming aggressive could occur at the same rate with which they occur during typical clinical care. Further, the population served by this intervention is by definition a vulnerable medical population experiencing dementia and often multiple other chronic illnesses. We would expect that due to the age and illness severity of the PLWD that the occurrence of falls, emergency room/hospitalizations, and death can reasonably be expected. Implementation team care partners are already trained by their specific facility in managing safety concerns and health events that may occur during typical care and they will behave the same during enrollment in the IPPI program. The care partners would act according to their facility's rules and expectations.

In the case of an adverse event occurring during study participation, an Adverse Event

form would be submitted to the PI within 3-days of the event (see procedural expectations below in 7.3). In the case of death of a resident, the site champion will be advised to call the PI to notify her of the passing.

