7.4 Safety Monitoring

The IPPI program does not entail risks to the NH resident or staff member. Each involved individual can refuse to participate at any time. The IPPI program is based on a preferred activity leading to a meaningful and enjoyable use of time between the resident and care partner.

The NIA IMPACT Collaboratory Safety Officer will oversee all data and safety monitoring activities for this study to evaluate the progress of the study, and to review procedures for maintaining the confidentiality of data, the quality of data collection, management, and analyses. Advarra IRB will conduct the ethical review required for the protection of human subjects.

In addition, all activities for this intervention will abide by expected Centers for Medicare and Medicaid Services Health and Safety care requirements within the NHs.

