11.2 Informed Consent Forms

Consent:

Nursing Home Residents: There will be no randomization process for this feasibility trial.

We are requesting a waiver of consent for resident participation in the study. This includes not only those that are exposed to the IPPI program itself, but for the release of EHR data for all NH residents in the study sites, regardless of participation/eligibility. The latter is because it would be challenging for the UCH IT staff to create a cohort-specific data extract for the project. We believe the waiver of informed consent is justified for the following reasons.

First, the research involves no more than minimal risk to subjects. Prior research has indicated there is minimal risk because this is a preference-based activity for the resident and should be a positive experience. The types of activities we are asking staff to engage residents in are usually done as part of standard care, but in a group setting.

Second, the research could not be practicably carried out without the requested waiver. It would not be practicable for care partners to seek informed consent from either the NH resident living with dementia or their legally authorized representative because the IPPI is a clinical process implemented to address a clinical need. For example, the moment a resident starts to be physically or verbally abusive to a staff member during care they need to have the ability to immediately start an IPPI activity. The IPPI activities would be integrated into the care process to address a clinical need. We do not think that residents or their legally authorized representative would object if they knew of the waiver and its intent in facilitating the research. We believe that most people would prefer to engage in activities they find meaningful and enjoyable on a one-to-one basis.

Third, we need to use identifiable private information and the research could not practicably be carried out without using such information in an indefinable format. Because we will need to link individual level data from multiple data sources (e.g., MDS and EMR) we will work with UCH IT to send the PI a crude dump of their system and the PI will link, deidentify the data and send to the statistical consultant.

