***email address will be used to identify if individual completed the Emotion Focused Communication Training**

IPPI Program – Resident Preferences Worksheet

Site champion(s) will maintain a password protected list of the name of each resident that is enrolled into the IPPI program along with a unique ID# that is determined by the champion(s). This password protected file will be shared with the PI who will then link the data from this worksheet to the electronic medical record data prior to deidentifying.

After completing a resident's preference assessment, identify and record their most important preferences in the column "Important Preferences." Next, review the list of IPPI protocols then record the protocols that match the resident's important preferences in the "Matching IPPIs" column. Review the list of matching IPPIs with the implementation team member(s) that will be facilitating the activity with the resident and let them chose which IPPI activities (1-2) they are most comfortable doing. After they've chosen the IPPI activities, record their selection in the "IPPIs Selected" column. Identify one or more resident behaviors that are the target outcome for the intervention as indicated on the MDS Section E. Finally, note if the resident completed the project and if there were any adverse events.

Resident Unique ID#	Important Preferences	Matching IPPIs	IPPIs Selected by implementation team	Supplies Needed Location	Which targeted behavior(s) do you hope the IPPI will remediate? Check all that apply	Did the resident complete the IPPI Project? Yes No If no, why did the individual not complete the project?	Did the resident have any adverse events? Yes No If Yes, complete Serious Adverse Event Report Form
	•	•	•	○	 Physical behavioral symptom  Verbal behavioral symptom  Other behavioral symptom  Rejection of Care  Wandering  Depressive Mood Symptoms	○	○

Observation Checklist of Fidelity to IPPI Protocol conducted by Champion

Did the person delivering the IPPI do any of the following?

1. Yes No N/A Introduce self to resident
2. Yes No N/A Introduce IPPI activity to resident
3. Yes No N/A Consider possible distractions (background noise, visual/tactile)
4. Yes No N/A Check that individual could hear or was wearing hearing aids if applicable
5. Yes No N/A Interrupt resident in the middle of a visit (reverse coded)

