6. Yes No N/A Give the resident a choice of two items/topics
7. Yes No N/A Ask open-ended questions
8. Yes No N/A Allow the resident time to respond to a question or complete a task
9. Yes No N/A Notice responsive behaviors (eye contact, facial expressions, gestures)
10. Yes No N/A Validate the resident's thoughts and feelings (echo words or gestures)
11. Yes No N/A Encourage the resident to do as much as possible independently
12. Yes No N/A Is the activity a positive emotional experience for the resident?
13. Yes No N/A Adapt to situation – if resident does not want to continue – change subject
14. Yes No N/A If resident becomes agitated, tries to calm them down
15. Yes No N/A Communicate that the session is over
16. Yes No N/A Thank the resident for participating
17. Yes No N/A Explain what is happening next

Serious Adverse Event Report Form Template

Protocol Title: Click or tap here to enter text.

Project ID: Click or tap here to enter text.

PI Name: Click or tap here to enter text.

Encrypted Site ID (e.g., site01, site02): Click or tap here to enter text.

Encrypted Subject ID (e.g., ptID001, ptID002): Click or tap here to enter text.

1. SAE Onset Timeframe (Two-month timeframe anytime within which the event occurred):
Click or tap to enter a date. **To** Click or tap to enter a date.

2. Duration of SAE (Number of days):
Click or tap here to enter text.

3. Location of adverse event:
 Emergency Department
 Hospital
 Outpatient visit

- Nursing Home/Skilled Nursing Facility
- Home
- Other, Specify: Click or tap here to enter text.
- Unknown

4. Was this an unexpected adverse event? Yes No

5. Brief description of participant:

Sex: Choose an item.

Age: Choose an item.

6. Adverse Event Term: Click or tap here to enter text.

7. Brief description of the nature of the serious adverse event (attach additional page if more space is needed.): Click or tap here to enter text.

8. Category of the serious adverse event:

- death
- life-threatening
- hospitalization - initial or prolonged
- disability / incapacity
- required intervention to prevent permanent impairment (Devices Only)
- important medical event

9. Intervention type:

- Behavioral/Life Style, Specify: Click or tap here to enter text.
- Device, Specify: Click or tap here to enter text.
- Education, Specify: Click or tap here to enter text.
- Medication Deprescribing, Specify: Click or tap here to enter text.
- Other, Specify: Click or tap here to enter text.

10. Intervention target:

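### Unanticipated problems include harm to others, but no safety prompt shown asks about it, and section 7.4's no-risk statement conflicts with section 7

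*Combined protocol and SAP*

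**What the plan says.** Section 7.3 sets three criteria for an unanticipated problem, all of which must be met: the event is unexpected in nature, severity or frequency; it is related or possibly related to the research; and it raises the known level of risk. The third reads "Suggests that the research places participants or others at a greater risk of harm". Under section 7.3.1 every UP goes to the IMPACT Collaboratory, the IRB, the NIA program officer and the Safety Officer within 48 hours of the study learning of it.

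The prompts that feed this rule are worded around the resident. On monthly calls the team is asked: "Have there been any unexpected changes in resident behaviors or health while participating in the study". The last column of the Resident Preferences Worksheet (Appendix A) asks: "Did the resident have any adverse events".

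On risk, section 7.4 states: "The IPPI program does not entail risks to the NH resident or staff member". The opening of section 7 instead describes the risk to the organization, residents and care partners as minimal, and says an activity can be stopped if the resident or the care partner becomes distressed.

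**The concern.** The reporting rule is wider than the questions meant to supply it. The 48-hour clock starts only when the study knows of an event, and nothing shown in the documents is designed to produce that knowledge when the injured person is not an enrolled resident.

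The protocol's own description makes the gap relevant. Section 9.1 lists physical, verbal and other behavior aimed at other people among the Section E items. Those items can qualify a resident for enrollment and can be chosen as the target. Section 5.1 allows sessions in common areas. Section 7 accepts that "behaviors such as wandering or becoming aggressive could occur" during a session, at the usual-care rate. Section 11.2 justifies the consent waiver with an example in which staff must be able to start an IPPI "the moment a resident starts to be physically or verbally abusive to a staff member during care".

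At stake is what the pilot can say about safety for the people who deliver the program and those nearby. If nobody is asked, an absence of reports is weak evidence. Harm to staff also bears on feasibility, and section 9.2 says the pilot is to guide a full-scale effectiveness trial.

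**Working it through.** No power, rate or error calculation applies. The check compares the definition with each route by which an event could reach the study.

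| Place | What it covers | Asks about care partners, non-enrolled residents or visitors? |
|---|---|---|
| 7.3, UP definition | Participants or others | Yes, by definition |
| 7.3, AE definition | "Any unfavorable medical or behavioral outcome in a clinical research study participant"; an SAE is a subset of AEs | No; whether staff count as participants is unclear |
| 7.3, monthly script | The resident's behavior or health | No |
| Appendix A, worksheet column | The resident's adverse events | No |
| Appendix A, SAE template | Subject ID and "Brief description of participant" | No field; the staff and care-partner boxes record the intervention target, not who was harmed |
| 7.3.1, reporting steps | Begin from an AE or SAE; relatedness is weighed against the resident's medical status | No |
| 9.3, safety review | Prompted by repeated AEs or SAEs | No |
| 7.1, 10.3.2 and 10.3.4, calls and notes | General concerns, barriers, deviations | Only if volunteered |
| 7.1 to 7.3, the homes' own procedures | Continue as usual | No stated route to the PI for someone who is not enrolled |

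**Result.** Three prompts can be read in the documents. Two name only the resident. The third is written for a participant and has no place for an injured non-participant. UPs appear in the definition and in the onward-reporting rules, but no step tells a site how to recognise one or send it in.

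**Exposure.** Inputs are 105 to 110 residents (Précis, Sample Size and Population) and 48 sessions per resident (Adherence Assessment).

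- Lower: 105 × 48 = 5,040 sessions.
- Upper: 110 × 48 = 5,280 sessions.

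This counts planned contacts at full delivery. It is not an estimate of missed harm.

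**What would count as a UP.** An injury to another enrolled resident already falls under the AE definition. An injury to anyone else must still meet all three criteria. Because section 7 foresees aggression at the usual-care rate, many injuries would fail the unexpectedness test. Those that pass would do so on nature, severity or frequency, and frequency cannot be judged without a count.

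**The risk statements.** Section 7.4 denies risk to resident and staff without qualification. Section 7 calls the risk to care partners minimal, which is a direct conflict. Section 7 also allows for agitation and aggression during a session. It claims no excess over usual care, but that is still not the same as no risk.

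**The case against.** The strongest reply is that the UP definition covers any incident and does not depend on the AE forms. The clock starts when the study learns of the event by any route, and routes exist. Monthly calls invite the team to raise concerns (7.1, 10.3.2), notes of barriers are kept (10.3.4), and exit interviews ask about barriers. The people on those calls are the ones delivering sessions, so the party most exposed is already in contact with the study. An enrolled resident who uncharacteristically strikes a care partner may be a behavioral AE, and its description could mention the person hurt. The homes keep their regulated procedures, and a Safety Officer oversees a descriptive, minimal-risk pilot.

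Much of this stands. A reader might infer that such injuries are never captured, or that the UP rule cannot operate for anyone but the resident. The documents do not support either reading, because the open routes could bring an event to light and the rule would then apply. A reader might also infer that every form omits the question. That cannot be verified: the separate Adverse Event form and the exit interview guide are named but not reproduced in the text available.

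What the reply does not do is supply a direct question. The open routes depend on someone volunteering the event, and section 10.3.1 says implementation-team staff receive no human subjects research training, so a site may not see a staff injury as reportable. The help line in 7.1 is for adapting an activity. The SAE template says participant rather than resident, which might be stretched to staff, but section 11.2 says the team is not consented as study subjects.

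**Conclusion.** The point holds as a gap in systematic capture. The UP definition reaches people other than participants, while the prompts shown do not ask about care partners, non-enrolled residents or visitors. For them the definition relies on spontaneous report, or on facility processes with no stated path to the PI. The 7.4 sentence separately conflicts with section 7 and needs reconciling whatever is decided on capture.

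The size in events is unknown, because the documents give no rate; the exposure figure shows only how many contacts go without a direct question. No planned outcome or analysis depends on these events, so the consequence is limited to safety reporting and what can be claimed from it. The conclusion assumes that the Adverse Event form not shown has no such question. If it has one, the gap narrows to the call script and the worksheet.

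**What to change.** 1. Add one line to the monthly call script and to the worksheet, and to the Adverse Event form if it lacks one: was any staff member, other resident or visitor hurt or threatened during, or because of, an IPPI? Record the date and a brief description.
2. Screen each yes against the three UP criteria in section 7.3, and report the count with the other safety data even when none qualifies.
3. Reconcile the section 7.4 sentence with section 7, so that the protocol makes one consistent statement about risk to residents and care partners.

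The cost is one question per call, one form line and a short amendment. The downside is a few extra reports and a slightly less favourable risk statement.

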7.3.1 Reporting Procedures

In the occurrence of an AE or SAE, during an IPPI, the implementation team will be instructed to complete the column in the provided binder on the final column of the resident preferences worksheet, providing a description of the event, the timing of the event, and the anticipated clinical response. If warranted, the team will be instructed to complete the IMPACT Serious Adverse Event (SAE) Report Form.

If an AE or SAE becomes apparent during a monthly call, the PI will request a completion of an Adverse Events or IMPACT Serious Adverse Event (SAE) Report Form, as applicable.

In the case of death, the site champion will also be instructed to call the PI to relay this information.

Following typical clinical safety protocols of the specific NH, a determination of continuation in the IPPI program will be determined by the NH clinical implementation team based on severity of event and relationship to the study. The decision for care alteration or necessary withdrawal from the study will be communicated with the PI through the Adverse Events form and/or if necessary, the second to last column of the Resident Preferences Worksheet. That column asks if the resident completed the IPPI program and if no, why not. For reporting, the decision of relatedness, expectedness, and severity of events will be defined as follows:

Severity of Event

All AEs will be assessed by a qualified medical professional on the NH implementation team using a protocol defined grading system to describe severity.

- Mild – Awareness of signs or symptoms, but easily tolerated and are of minor irritant type causing no loss of time from normal activities. Symptoms do not require therapy or a medical evaluation; signs and symptoms are transient.
- Moderate – Events introduce a low level of inconvenience or concern to the participant and may interfere with daily activities but are usually improved by simple therapeutic measures; moderate experiences may cause some interference with functioning.
- Severe – Events interrupt a participant’s usual daily activity and may require systemic treatment. Severe events are usually potentially life-threatening or incapacitating. Of note, the term “severe” does not necessarily equate to “serious”.

Expectedness

- Unexpected - Nature or severity of the event is not consistent with information about the condition under study or intervention in the protocol, consent form, product brochure, or investigator brochure.

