- Expected - Event is known to be associated with the intervention or condition under study.

Relationship To Study Intervention

In the case of an AE, a qualified clinical professional on the implementation team at the resident’s NH will help judge the relationship of the AE to the study intervention. In light of the medical status of the resident participating in the study, the qualified clinical professional, will evaluate the degree to which the event was related to underlying disease/concurrent illness or study-related procedures, accidents, and other external factors. The clinician will indicate “Yes” in the final column of the Resident Preferences Worksheet and complete the Serious Adverse Event Report Form Template:

- Definitely Related – There is clear evidence to suggest a causal relationship, and other possible contributing factors can be ruled out. The clinical event occurs in a plausible time relationship to the IPPI intervention, follows a known or expected response pattern to the suspected intervention, that is confirmed by improvement on stopping and reappearance of the event on repeated exposure, and that could not be reasonably explained by the known characteristics of the subject’s clinical state. Depending upon severity of AE, the clinician may judge the event to warrant withdrawal from the study.

- Possibly Related – There is some evidence to suggest a causal relationship (e.g., the event occurred within a reasonable time after an IPPI happened or follows a known or expected response pattern to the suspected intervention). However, other factors may have contributed to the event (e.g., the participant’s clinical condition, other concomitant events). An AE rated as “possibly related” soon after discovery, can be flagged as requiring more information and later be upgraded to definitely related”, as appropriate.
- Not Related – The AE is clearly not related and completely independent of study intervention administration, and/or evidence exists that the event is definitely related to another etiology. For example, another cause of the event is most plausible and/or a clinically plausible temporal sequence is inconsistent with the onset of the event and the study intervention and/or a causal relationship is considered biologically implausible

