All adverse events that are serious (SAE) and unexpected (i.e., have not been previously reported for the study’s intervention) will be reported to the IMPACT Collaboratory Regulatory and Data Team Leader ([name]), NIA IMPACT Collaboratory PO ([name]), and the IMPACT Collaboratory Safety Officer within 48 hours of the study’s knowledge of SAE.

- Only those adverse events that are serious (SAE), unexpected, and related to the intervention must also be reported to Advarra IRB. Unexpected and unrelated SAEs will be reported to Advarra IRB on a case-by-case basis if requested by the IMPACT Collaboratory Safety Officer or NIA IMPACT Collaboratory PO.

All deaths will be reported to IMPACT Collaboratory Regulatory and Data Team Leader ([name]), NIA IMPACT Collaboratory PO ([name]), and the IMPACT Collaboratory Safety Officer within 24 hours of study’s knowledge of death.

- Advarra IRB does not require the specific reporting of death outside of the SAE reporting requirement above, but they will be notified on a case-by-case basis if requested by the IMPACT Collaboratory Safety Officer or NIA IMPACT Collaboratory PO.

All unanticipated problems (UPs) will be reported to the IMPACT Collaboratory Regulatory and Data Team Leader ([name]), Advarra IRB, NIA IMPACT Collaboratory PO ([name]), and the IMPACT Collaboratory Safety Officer within 48 hours of the study’s knowledge of the event.

The summaries of all previously reported unexpected and related SAEs, deaths, and UPs, as well as all other SAEs and AEs will be reported to IMPACT Collaboratory Regulatory and Data Team Lead ([name]), Advarra IRB, NIA IMPACT Collaboratory PO ([name]), and the IMPACT Collaboratory DSMB Chair (or the project’s Safety Officer) at a minimum every 6 months, or at a frequency requested by the IMPACT Collaboratory Safety Officer or NIA IMPACT Collaboratory PO.

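### The scripted monthly safety question covers only unexpected changes, and two meanings of unexpected in section 7.3.1 can give the same non-fatal hospitalization different reporting deadlines

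*Combined protocol and SAP*

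**What the plan says.** Section 7.3 defines an adverse event as any unfavorable medical or behavioral outcome. It lists falls among its examples and sets no condition that the event be unexpected. It then says that, given residents' age and illness, "the possibility of falls, emergency room/hospitalizations, and death can reasonably be expected". The next sentence says of the monthly calls that "we will ask if any adverse events have occurred", and supplies the words to be spoken: "Have there been any unexpected changes in resident behaviors or health while participating in the study".

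Section 7.3.2 describes the monthly contact again. There the PI asks about adverse and serious adverse events since the last call, with no mention of expectedness.

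Section 7.3.1 defines an unexpected event under its Expectedness heading: "Nature or severity of the event is not consistent with information about the condition under study or intervention in the protocol" or in related study documents. The matching definition of expected is: "Event is known to be associated with the intervention or condition under study". Later in 7.3.1, the 48-hour rule applies to events that are "serious (SAE) and unexpected (i.e., have not been previously reported for the" study's intervention. Serious events that are unexpected and also related must go to the IRB. All other adverse and serious adverse events go into a summary at least every 6 months, or as often as the Safety Officer or program officer asks. All deaths are reported within 24 hours.

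**The concern.** The spoken question is narrower than the purpose stated just before it. A site told that falls and hospital visits are to be expected can answer no after either, and the answer is truthful. The monthly call is the active prompt for events that a form has missed, so its wording matters.

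The second problem comes after an event is known. The word *unexpected* decides whether a serious event goes to the Safety Officer within 48 hours, and it is one condition for IRB reporting. With two meanings in the same section, two people following the protocol can send the same event down different paths.

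At stake are complete collection and consistent sorting of expected events. Section 9.3 provides for a safety review if adverse events linked with the study recur, and the definition of an unanticipated problem in 7.3 includes unexpected frequency. Both are harder to judge if expected events are collected or classified unevenly.

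**Working it through.** No arithmetic decides this point; the check is a side-by-side reading of the rules.

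**Step 1: what the monthly call asks.**

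| Place | Scope of the inquiry |
|---|---|
| 7.3, adverse event definition | Any unfavorable outcome, falls included |
| 7.3, lead-in to the script | Any adverse event |
| 7.3, script | Unexpected changes only |
| 7.3.2 | Any adverse or serious adverse event since the last call |

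Three of the four are unrestricted. The exception is the only one that gives words to be spoken.

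**Step 2: what else would pick up an omitted event.**

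- Section 7: an Adverse Event form to the PI within 3 days of an event during study participation.
- Section 7.3.2: champions record reportable events from enrollment until 7 days (non-serious) or 30 days (serious) after participation ends.
- Appendix A: the Resident Preferences Worksheet asks whether the resident had any adverse event.
- Section 8: withdrawals, including those after hospitalization, go to the PI with date and reason.

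None of these depends on the script, but some have limits. The binder instruction in 7.3.1 is worded for events during an IPPI session, and the schedule in 6.1 marks the Adverse Events form only in the per-session column. Two 10-minute sessions a week are 2 × 10 = 20 minutes out of 7 × 24 × 60 = 10,080, or 20 / 10,080 ≈ 0.2% of the week. This is a share of time, not an event rate. Section 16 has binder forms arriving in batches with the 3- and 6-month data. Sections 7 and 7.3.2 are broader, so the other routes are real, though not all are prompt.

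**Step 3: which deadline applies under each meaning.** Meaning A is the Expectedness definition; meaning B is the parenthesis in the 48-hour rule.

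| Event | Meaning A | Meaning B |
|---|---|---|
| Death | 24 hours | 24 hours |
| Non-fatal hospitalization, or fall meeting a seriousness criterion, not reported before for the intervention | Expected: periodic summary | Unexpected: 48 hours |
| Same event, already reported for the intervention | Expected: periodic summary | Not unexpected: periodic summary |
| Fall meeting no seriousness criterion | Periodic summary | Periodic summary |

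The meanings disagree in the second row only. Under A, the event counts as expected because 7.3 itself says such events go with this population, provided its nature and severity fit that description. Under B, the answer depends on reporting history, so the first event of a kind may be unexpected and a later one not. The table leaves aside events that qualify as unanticipated problems, which are due within 48 hours by their own rule.

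**The case against.** The strongest reply is that the script is one loosely worded example inside an inquiry that is unrestricted in both 7.3 and 7.3.2, and that several routes in step 2 work whatever is said on the call. That is largely right: the literal script has a gap, but the ascertainment plan as a whole does not miss these event types.

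A reader might go further and infer that the commonest serious events, deaths included, can go both unasked and unexpedited. The documents do not support that. Every death prompts a call to the PI and is reported within 24 hours regardless of expectedness. No event rates are given, so commonest cannot be shown, and a fall is serious only if it meets a listed criterion. Nor do the documents say that the monthly call is the main route for events outside sessions.

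It is also fair to say that placing expected serious events in a periodic summary is a deliberate rule, that 6 months is the longest default interval and can be shortened on request, and that the conflict over *unexpected* depends on what has already been reported for the intervention, which the documents do not state. These points limit the finding. They do not reconcile the script with its stated purpose, or the two definitions with each other.

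**Conclusion.** Two inconsistencies stand, both in rules as written rather than in missing detail.

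First, the script in 7.3 is narrower than its own lead-in, than the adverse event definition and than 7.3.2. Its effect is confined to non-fatal events at the monthly prompt, with other routes in place.

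Second, the two meanings of *unexpected* in 7.3.1 can put a non-fatal hospitalization, or a fall meeting a seriousness criterion, either inside the 48-hour rule or outside it. Outside, it waits for a summary due at least every 6 months. This rests on the assumption that the event has not been reported before for this intervention; if it has, the meanings agree. The number of residents affected cannot be estimated from the documents.

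The change is worth making because it is small and improves safety collection and reporting. It is not evidence that the plan leaves serious events unmonitored.

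**What to change.** Reword the scripted question in 7.3 to match its lead-in and 7.3.2, for example: *Since the last call, has any enrolled resident had an adverse or serious adverse event of any kind, including a fall or an emergency or hospital visit, whether or not it was expected?*

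Reconcile the Expectedness definitions in 7.3.1 with the parenthesis in the 48-hour rule, so that one definition of *unexpected* governs both that rule and reporting to the IRB. Which definition to keep is for the sponsor and the Safety Officer to settle.

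The cost is one question and one definition. Sites would log somewhat more expected events, but 7.3.2 already requires all adverse events to be documented. The number of 48-hour reports would depend on the definition kept.
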